10.2. Data Analysis Plan

The co-primary outcome variables will be peak VO₂ and work performed during a symptom-limited maximal effort exercise test. All secondary outcome measures are continuous variables. The predictor of interest for all aims will be intervention (KNO₃ therapy vs. placebo), with analyses based upon the total number of subjects randomized. Initial descriptive estimates of all measures will be generated for study participants at each time point by treatment group. Statistics will include estimates of central tendency, measures of variability, and derived moments of skewness and kurtosis. Analyses of distributional properties will be performed to determine if variance stabilizing or normalizing transformations should be applied. Outliers will be assessed via visual inspection of distributions and checked for accuracy. Aim 1 will assess the effects of potassium nitrate therapy on peak O_2 / work performed (co-primary outcomes) and quality of life score (secondary outcome). An initial assessment of the treatment effect will be performed using the paired t-test and the non-parametric Wilcoxon sign-rank test on the difference between the paired within subject outcome measures. This will be followed by a more comprehensive linear mixed-effects model analysis¹⁵⁸ allowing for assessments of the treatment effect on each continuous outcome of interest while controlling for effects of other covariates such as period, sequence, and a random subject effect nested within sequence. For non-normal distributed outcomes, we will utilize nonparametric methods or consider distribution-stabilizing transformations. The intervention groups will initially be compared within each period (time invariant covariates will only be compared for period 1) according to continuous covariates described above using parametric or non-parametric one-way ANOVA models, depending upon whether or not normality appears to be in question. Levine's tests will be used to assess homogeneity of variance. Additionally, the intervention groups will be compared within period according to categorical covariates using Fisher's Exact tests. Significant differences between groups on these variables will result in their use as control variables in the modeling of outcome. Separate models will be generated for each of the two outcome measures, with each outcome measure regressed on intervention group assignment, along with baseline outcome and any other covariates deemed prognostic in preliminary analyses. The linear mixed-effects models will incorporate adjustments for any period effect and include data from dropouts.¹⁵⁹⁻¹⁶¹ The model will include subject-specific intercepts as random effects, and assumes independent and identically distributed random errors within subject. Restricted maximum likelihood estimation will be used, and an appropriate covariance matrix will be specified. Model assumptions will be examined (eg,QQ plots to assess normally distributed residuals for valid Wald tests). All mixed-effects models will be analyzed using the SAS PROC MIXED procedure¹⁶² in SAS version 9.3 (SAS Institute, Inc., Cary, NC). We will make every possible effort to minimize missing data and ensure final assessments for participants opting to discontinue study participation. Missing data, however, is an inevitable problem in a longitudinal study. The mechanism for missingness-missing completely at random (MCAR), missing at random (MAR), nonignorable or not missing at random (NMAR)-will be evaluated prior to implementing methodology intended to minimize bias from missing data.¹⁶³ We anticipate that ~10% of randomized subjects will not complete the study.

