
The intent-to-treat principle of including all randomized participants in the outcome models will be followed. SAS software procedures will be used for creating and analyzing multiple imputed data sets for incomplete multivariate data. Instead of filling in a single value for each missing value, Rubin's¹⁶⁴ multiple imputation procedure replaces each missing value with a set of plausible values that represent the uncertainty about the correct value to impute. These multiple imputed data sets are then analyzed using standard procedures for complete data and combining the results from this analysis. Assuming monotone missing data patterns emerge, either a parametric regression method that assumes multivariate normality or a nonparametric method that uses propensity scores will be implemented, depending upon distributional patterns.

Analytic methods described above will take advantage of all available data. The possibility of systematic bias in the outcomes for those who withdraw exists. Baseline characteristics will be compared among subjects with and without complete follow-up, recognizing that statistical power associated with finding true statistical differences may be limited. To assess potential biases, a comparison of withdrawal rates and or/time to withdrawal will be included. If the number of subjects lost to follow-up is small and the missing observations can be documented as being MAR or MCAR, then the primary hypotheses will be tested using the complete observed data. If missing observations cannot be assumed to be MAR or MCAR, more complex approaches will be considered. Sensitivity analyses for these models will be performed should they be implemented.¹⁶⁵

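### Section 10.2 allows propensity-score imputation that gives up the crossover's pairing for imputed subjects, and makes the primary test depend on a missingness condition that data cannot establish

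*Combined protocol and SAP*

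**What the plan says.** All of this is in section 10.2, Data Analysis Plan.

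- **Tests.** "An initial assessment of the treatment effect will be performed using the paired t-test and the non-parametric Wilcoxon sign-rank test". A mixed model, described as more comprehensive, follows. "The linear mixed-effects models will incorporate adjustments for any period effect and include data from dropouts". It has a random subject intercept and "assumes independent and identically distributed random errors within subject", although the plan also promises to specify a suitable covariance matrix.
- **Imputation.** Multiple imputation is planned. If the pattern is monotone, "either a parametric regression method that assumes multivariate normality or a nonparametric method that uses propensity scores will be implemented, depending upon distributional patterns". The variables in the imputation model are not listed.
- **Non-normal outcomes.** "For non-normal distributed outcomes, we will utilize nonparametric methods or consider distribution-stabilizing transformations".
- **Missingness mechanism.** The mechanism, whether MCAR, MAR or "nonignorable or not missing at random (NMAR)-will be evaluated prior to implementing methodology intended to minimize bias from missing data".
- **Complete-data rule.** If few subjects are lost (no threshold is given) and "the missing observations can be documented as being MAR or MCAR, then the primary hypotheses will be tested using the complete observed data". The next sentence uses a different standard: "If missing observations cannot be assumed to be MAR or MCAR, more complex approaches will be considered". Sensitivity analyses are promised for such models.

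**The concern.** Section 4.1 justifies the crossover by the reduction in between-subject variability. That gain comes from comparing each subject with himself or herself. The gas-exchange exercise test is described only at the two 6-week visits, so a subject's other-period result is the only same-endpoint predictor of a missing value. Propensity-score imputation uses that result only as far as it enters the score and shapes the score groups. If donors are pooled across sequences, they also mix the two treatments.

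The complete-data rule raises a different problem. Observed data can contradict MCAR, but they cannot show that missingness is MAR rather than NMAR. A rule that needs this documented leaves the route to the primary test to judgement after the data are seen.

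**Working it through.** **Inputs.** 84 randomized, 90% retention, effect 0.6 and SD of change 1.23 ml/kg/min, two-sided alpha 0.05, stated power 80% (section 10.1). About 10% non-completion, so about 8 of 84 (section 10.2). Pilot peak VO2 SDs 3.7 and 3.1; pilot total work 55.6±35.3 and 49.2±28.9 kJ (section 3.5.1).

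**The plan's own figure.** With 84 × 0.9 = 75.6 completers and 0.6/1.23 = 0.488, paired t-test power is 98.6% (n = 75) or 98.7% (n = 76), not 80%. This is a separate matter, but it makes 98–99% the reference here.

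**Strength of pairing.**
- Equal SDs: 1 − 1.23²/(3.7² + 3.1²) = 1 − 1.513/23.30 = 0.935.
- Pilot SDs: (23.30 − 1.513)/(2 × 3.7 × 3.1) = 21.787/22.94 = 0.950.

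**Hand check if pairing is wholly lost for 8 subjects.** Their SD of difference would be √23.30 = 4.83. The pooled value is √[(76 × 1.513 + 8 × 23.30)/84] = 1.89. The standardized effect is 0.6/1.89 = 0.32 and power about 82%, before between-imputation variance is added.

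**Simulation.** 42 per sequence; 8 missing period 2; MCAR, or MAR with missingness weight exp(−z) in the period-1 value (an assumption: ×2.7 per SD lower). Five score groups, approximate Bayesian bootstrap, 20 imputations, Rubin's rules, period-adjusted estimate, 2000 runs, true effect 0.60. SE and estimate use a common SD; power also covers SDs 3.7/3.1.

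| Route | SE | Power | Estimate |
|---|---|---|---|
| Complete pairs, REML or regression imputation | 0.14 | 98–99% | 0.60 |
| Propensity score, period-1 outcome only | 0.155–0.161 | 94–96% | 8–9% low |
| Propensity score, period-1 outcome and sequence | 0.171–0.182 | 87–93% | 3–6% low |
| Propensity score without period-1 outcome | 0.23–0.25 | 66–74% | no consistent direction |

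Adding a weak covariate (r = 0.2) to the third row gives SE 0.180–0.207 and power 81–89% (common SD). Right-skewed data (SD 61% of the mean) give, in table order, 97–98%, 91–96%, 87–95% and 73–80%. With 4 missing the figures are 99%, 98%, 97% and 86–90%. At a null effect under MCAR, two-sided rejection is 3.3–3.8% with the period-1 outcome in the score and 1.3% without it.

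**Could the route be triggered?** A normal distribution would put Φ(−55.6/35.3) = 5.8% and Φ(−49.2/28.9) = 4.4% of total work below zero. Non-normality of a co-primary endpoint is therefore plausible.

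**Complete pairs under MAR.** Write A for the nitrate value and C for the control value. With the pilot SDs, cov(A, C) = 21.787/2 = 10.89.
- Nitrate first: cov(A − C, A) = 13.69 − 10.89 = 2.80, or 2.80/3.7 = 0.756 per SD of the period-1 value.
- Control first: cov(A − C, C) = 10.89 − 9.61 = 1.28, or 1.28/3.1 = 0.414 per SD.

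Both are positive, so losing subjects with low period-1 values raises the mean difference in both sequences. Under weight exp(−kz) the lost subjects average about −k SD and the 76 completers about +8k/76. The shift is about (8k/76) × (0.756 + 0.414)/2 = 0.062k. That is 0.062 for k = 1, 0.043 for k = ln 2 and 0.025 for k = ln 1.5. Simulation, which samples without replacement, gives 0.056–0.057, 0.037 and 0.023–0.024. Two-sided rejection at the null is 6.9–7.3% at k = 1 and 5.4–5.7% under the weaker settings. With equal SDs the two covariances are equal and opposite and the shift cancels; under MCAR there is none.

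**Mixed model as written.** In simulation at k = 1, i.i.d. errors leave the estimate at 0.650–0.656. Treatment-specific variances give 0.604, with power 98.8%. Because 10.89 exceeds the control variance 9.61, a random intercept with unequal residual variances cannot fit these pilot moments. An unstructured 2×2 matrix can.

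**The case against.** The propensity route needs a monotone pattern, non-normality, no transformation, and no use of the complete-data rule or mixed model in its place. Section 10.2 plans distributional checks to decide on transformations. In a monotone pattern the period-1 outcome is the natural predictor, and with it in the score power stays above 80%. All of this stands. A reader might infer that the plan commits to this method, that the trial becomes underpowered, or that false positives rise. The documents support none of these: the method is one option, a clear shortfall needs the period-1 outcome left out, and the test is conservative.

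A reader might also infer that no principal analysis exists, or that NMAR is ignored. The mixed model is plainly the fuller analysis and uses dropout data, a suitable covariance is promised, and sensitivity analyses for non-MAR models are planned. The missing label and the undefined threshold for few losses are missing detail.

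The complete-data rule may mean all observed values without imputation, which fits the plan's aim of using all available data. The complete-pairs figures apply only under the other reading. The upper tail alone would look worse (4.9–5.3% against 2.5%), but the plan tests two-sided.

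What remains is a stated option that is inferior in this design, and a gate that cannot be operated.

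**Conclusion.** The point holds in a limited form. Propensity-score imputation, if chosen, raises the SE for peak VO2 from 0.14 to about 0.155–0.18 with the period-1 outcome in the score (power 87–96%, estimate 3–9% toward zero). Without it the SE is 0.23–0.25 and power about 66–74%. The cost is precision and mild attenuation, not type I error.

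The MAR/MCAR gate cannot be met from data. If the rule means complete pairs, the exposure is about +0.02 to +0.06 ml/kg/min and two-sided error of about 5.4–7.3%, depending on an assumed MAR strength. It requires unequal treatment SDs, and the pilot difference may be chance.

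These figures assume 8 losses, all in period 2, and 1.23 as the SD of the paired change, as section 10.1 states. If 1.23 were instead a within-subject SD (SD of difference 1.74), regression imputation would give 84% power and propensity imputation 72–79% with the period-1 outcome, 58–59% without. No power figure is given for total work, because the documents give no SD of its change. This should be changed, but it does not invalidate the trial.

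**What to change.** In section 10.2:

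- Delete the propensity-score option.
- Name the REML mixed model on all observed period outcomes of all randomized subjects as the primary analysis for both co-primary endpoints. State MAR as an assumption and remove the requirement that it be documented.
- Replace i.i.d. within-subject errors with an unstructured 2×2 covariance by treatment, not a random intercept with unequal residuals.
- If multiple imputation is kept, use regression or predictive mean matching, on a transformed scale if skewed, with the other-period outcome, sequence and their interaction.
- Specify a delta-adjusted NMAR analysis. This only makes concrete the sensitivity analyses already promised.

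The cost is wording; no subjects, visits or procedures are added. The documents do not show whether data were unblinded: Appendix 2 anticipated analysis-ready data in April 2020, and Version 12 is dated October 2021. If they were, date the change and disclose that it was made after unblinding.

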10.3. Subgroup analyses and considerations about sex

Although women represent 60% of patients with HFpEF, our sample will include 50% women and 50% men. This is due to the fact that we explicitly wish to perform sex-stratified analyses, in

addition to testing for a potential modifying effect of sex on the effects of KNO₃. Having an equal balance in terms of the number of males and females maximizes the statistical power to test for significant interaction effects between sex and other variables of interest. Furthermore, the slight increase in the proportion of males sampled will help to maximize the statistical power for sub-analyses including only males. Balancing the sample on sex will also reduce the chances of having confounding between the race effect and other variables in the model. Lastly, since the over sampling of males is only slightly above the estimated actual population of 40%, the results of the analysis of the sample data should still be generalizable to the overall HFpEF population.

Additional pre-specified subgroup analyses will include diabetes vs. no diabetes, hemoglobin value above and below median, and use vs. non-use of calcium channel blockers.

10.4 Cardiac MRI sub-study analysis and power calculations

The aim of this ancillary study is to assess the paired difference in myocardial blood flow and perfusion reserve in response to KNO₃ or the control intervention (KCI) in a cross-over design. We will therefore utilize paired-t tests to estimate the difference. The non-parametric Wilcoxon sign-rank test will be considered, as appropriate. For exploration of the relationship between MPR and myocardial fibrosis or myocardial function, we will compute Pearson's correlation coefficients for linear associations, or the Spearman's Rank Correlation coefficient for monotonic non-linear associations. A p-value less than 0.05 will be considered significant.

Power calculations: The standard deviation of the change in MPR in repeated measures in prior studies is 0.5. Assuming a dropout rate of 10% (effective n=18), the ancillary study will have 85% power to detect a standardized effect size of 0.75 or greater. Therefore, our study will be powered to detect an improvement of 0.375 in MPR with KNO₃ vs. KCl.

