The sub-study will test the hypothesis that KNO_3 administered over a period of ~4-6 weeks, will improve MP and MPR in subjects with HFpEF as compared to KCI. We will also explore whether MPR (measured during the placebo intervention, KCI) correlates with increased myocardial fibrosis (measured as the extracellular volume [ECV]) using cardiac MRI), and with subclinical myocardial dysfunction (measured by impaired systolic/diastolic strain) in this population.

We plan to enroll up to 20 subjects in this ancillary study. Subjects participating in the ancillary study will undergo all procedures per the parent trial, but in addition, will undergo a stress perfusion cardiac MRI study during the last 2 weeks of phase 1 and phase 2, during which MP, MPR values, myocardial fibrosis and myocardial strain measurements will be obtained. Of note, this may occur either before or after the exercise endpoint assessment, based on schedule availability. We anticipate that this substudy will contribute to a better characterization of the effects of inorganic nitrate therapy on the myocardium.

Effects of KNO₃ Compared to KCI on Oxygen UpTake in Heart Failure with Preserved Ejection Fraction (KNO₃CK OUT HFpEFp)
National Heart, Lung and Blood Institute, National Institutes of Health
Phase IIb Randomized Clinical Trial (RCT)
84
University of Pennsylvania, Northwestern University, and the Corporal Michael J. Crescenz Veterans Affairs Medical Center
Randomized, double-blinded, placebo-controlled crossover study
Potassium Nitrate (KNO ₃) capsules, at a dose of 6 mEq (1 capsule) three times daily for approximately 6 weeks, versus, potassium chloride (KCI) capsules administered at a dose of 6 mEq (1 capsule) three times daily for approximately 6 weeks
To assess whether KNO_3 therapy improves exercise capacity, quantified as: (1) Total work performed during a maximal-effort exercise test; (2) Peak oxygen consumption (VO ₂) during a symptomlimited maximal effort exercise test. These will be the co-primary endpoints of the trial.

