10. STATISTICAL CONSIDERATIONS

10.1. Power calculations

We will randomize 84 subjects to one of 2 sequences (i), each of which consists of 2 periods (AB/BA design). We now have pilot data regarding the distribution of the changes in peak VO_2 (the primary endpoint of the study) as well as various secondary endpoints, among patients with HFpEF. We considered an increase in peak VO₂ of \sim 0.6 ml/kg/min to be the minimum clinically significant change. This was based on the fact that even "modest" changes of comparable magnitude in peak VO₂ have been associated with improved outcomes.¹⁵⁶ The standard deviation of the change in peak VO₂ in our pilot trial was 1.23 ml/kg/min. Therefore, the standardized effect size is 0.49 or greater. Assuming a 90% retention rate, enrolling 84 subjects in this cross-over trial will have 80% power to detect such an effect size in the intervention induced change of our study endpoints, with a two-sided α =0.05. Based on the distribution of the changes in study endpoints in our pilot trial or from repeated measurements of the Kansas City Cardiomyopathy Questionnaire in HFpEF patients, we estimated that this trial study is powered (80%) to detect the following changes in other endpoints: 4.6 points for the Kansas City Cardiomyopathy Questionnaire, 8.2% for exercise vasodilatory reserve, 19% for cardiac output reserve, 5 seconds for PCr/Cr recovery kinetics, and 4.2% change in reflection magnitude. We note that these differences are well below what is considered a clinically significant change in KCCQ (10 points or more, http://cvoutcomes.org/pages/3217) or the effect size that has been observed for these endpoints in our pilot trial.¹¹¹ Therefore, we are confident that we will achieve adequate power not only for our clinical endpoints, but also for our physiologic measures. PASS11157 was used to perform power analyses.

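### The cardiac MRI sub-study's paired t-test has no period term, so a period effect would cost power, or would shift the estimate if the sequence split among about 18 completers is uneven

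*Combined protocol and SAP*

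**What the plan says.** Section 10.4 sets out the sub-study's own analysis. The aim is to "assess the paired difference in myocardial blood flow and perfusion reserve in response to KNO₃ or the control intervention". The method follows directly: "We will therefore utilize paired-t tests to estimate the difference". The fallback has the same structure: "The non-parametric Wilcoxon sign-rank test will be considered, as appropriate". The threshold is "A p-value less than 0.05 will be considered significant". No period or sequence term appears, and the section does not refer back to Section 10.2.

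For the same AB/BA design, Section 10.2 uses the paired t-test and signed-rank test only as a first look. It then fits a linear mixed model "controlling for effects of other covariates such as period, sequence, and a random subject effect nested within sequence".

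Section 5.2 blocks the randomization of sequence by site, sex and ethnicity. Participation in the sub-study is not a stratum. Up to 20 subjects at two of the three sites may take part.

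The power statement in Section 10.4 concerns MPR only: "The standard deviation of the change in MPR in repeated measures in prior studies is 0.5". With 18 effective subjects it claims 85% power for a difference of 0.375. The hypothesis in Section 1 is that KNO₃ "will improve MP and MPR in subjects with HFpEF as compared to KCI", with neither endpoint ranked first.

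**The concern.** In an AB/BA crossover, a subject's KNO₃ minus KCl difference contains the treatment effect plus the period effect for one sequence, and minus it for the other. A paired t-test pools these differences without regard to sequence. If the sequences are equal in number, the period effect cancels from the mean but stays in the variance and costs power. If they are unequal, part of it remains in the estimate.

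The main trial's model handles this; the sub-study's plan stops at the step before. The sub-study is also where balance is least protected. It is a small opt-in group with its own entry conditions (Sections 4.3.4 and 11.3.7), and a finding on the first cardiac MRI can end participation before phase 2 (Section 4.3.3). At stake is how far a modest MPR difference from about 18 people can be read as a treatment effect.

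A smaller matter is that two endpoints are tested at 0.05 and neither is labelled as leading.

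**Working it through.** **Inputs.** From Section 10.4: SD of the within-subject MPR difference 0.5, 18 completers, target 0.375. Section 10.4 does not state sidedness. Two-sided 0.05 is taken from Section 10.1 ("with a two-sided α =0.05"). Assumed, because the documents give nothing: a period effect π (phase 2 minus phase 1) of 0.2 to 0.3 MPR units, and the sequence split n1:n2.

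**The plan's own figure.** 20 × 0.9 = 18 and 0.375 / 0.5 = 0.75. Paired t-test with 17 df and noncentrality 0.75 × √18 = 3.18: power 85.04%. The stated 85% reproduces.

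**How likely is an uneven split?**

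| Split | Random 18 of 84 split 42/42 | Independent coin flips |
|---|---|---|
| exactly 9:9 | 21% | 19% |
| 11:7 or worse | 43% | 48% |
| 12:6 or worse | 18% | 24% |

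The first column is hypergeometric and gives some credit to blocking. The second is binomial and gives none.

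**Shift in the unadjusted estimate.** Given the split, the mean difference is off by π × (n1 − n2) / 18.
- 9:9: zero.
- 11:7: 4/18 of π, which is 0.044 to 0.067.
- 12:6: 6/18 of π, which is 0.067 to 0.10. Divided by 0.375, that is 18% to 27% of the target.

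**Extra noise at 9:9.** The expected variance of the pooled differences is 0.25 + π² × 4 × 9 × 9 / (18 × 17) = 0.25 + 1.059π².
- π = 0.2: 0.292, SD 0.54.
- π = 0.3: 0.345, SD 0.59.

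Simulated power of the planned test falls from 85% to about 81% and 75%.

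**Type I error of the planned test, given the split (simulated, π = 0.2 to 0.3).**
- 9:9: about 3.6% to 2.3%.
- 11:7: about 4.8% to 4.4%.
- 12:6: about 6.4% to 7.4%.
- 13:5: about 8.7% to 12.4%.

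Averaged over the possible splits it is about 5.0% under coin flips, and 4.4-4.7% for a random subset of 84.

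**Period-adjusted analysis.** The estimate is the average of the two sequence-specific mean differences. SE = (0.5 / 2) × √(1/n1 + 1/n2), with 16 df.

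| Split | SE | 0.375 / SE | Power |
|---|---|---|---|
| 9:9 | 0.118 | 3.18 | 84.8% |
| 12:6 | 0.125 | 3.00 | 80.4% |
| 13:5 | 0.132 | 2.85 | 76.3% |

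These powers, and a type I error of 5%, hold whatever the period effect is.

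**Two endpoints.** Two independent tests at 0.05 give 1 − 0.95² = 9.75%. At assumed correlations of 0.5 to 0.9 the figure is 9.1% to 7.0%.

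**The case against.** A reader might infer that a period effect necessarily contaminates the treatment estimate, or that the planned test inflates false positives in general. The documents support neither. Sequence is randomized, so the expected imbalance is zero and the paired estimate is unbiased over randomization. Averaged over possible splits, type I error is at or below 5%. Even at 11:7 it is not inflated. The bias is conditional: it needs both a period effect and an uneven realized split. That stands, and it limits the point.

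Two further objections stand. Blocking within site gives some protection, so the coin-flip figure of 24% for 12:6 or worse is probably too high. And no document gives a period effect on MPR. The assumed 0.2 to 0.3 is 40-60% of the SD of differences, and a learning effect is hard to argue for a ratio measured under a drug vasodilator.

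A reader might also infer a familywise error of 9.75%. That needs independent tests, but Section 8.9 computes MPR from myocardial perfusion. If the Section 1 hypothesis means that both endpoints must improve, there is no inflation at all. MPR is the only powered endpoint and so the implied lead. What is left is a missing label.

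What these objections do not remove is that the analysis uses the observed split, which will be known. Once it is known to be 12:6, unbiasedness over splits that did not occur is little comfort. The protocol itself adjusts for period in the same design elsewhere.

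**Conclusion.** The point holds in a limited form. Section 10.4 omits the period adjustment that Section 10.2 applies to the main trial, and nothing ensures an even sequence split among sub-study completers.

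Under an assumed period effect of 0.2 to 0.3 MPR units, the consequence is either lost power (85% to about 81-75% at 9:9) or a shifted estimate (0.07 to 0.10 at 12:6, with type I error about 6.4-7.4%). The chance of 12:6 or worse is about 18% if completers are a random subset of 84 split 42/42, and 24% under coin flips. With no period effect there is no harm.

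The 85% power figure is right and should not be read as an error. The unranked endpoints are a minor labelling matter. The co-primary endpoints are untouched. Priority is low to moderate.

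**What to change.** In Section 10.4, make the main sub-study analysis a period-adjusted crossover analysis, with treatment and period as fixed effects and subject as random. For subjects with both scans this equals comparing within-subject period differences between the two sequences. The non-parametric alternative should be the rank-sum test on those period differences, because the signed-rank test has the same gap as the paired t-test.

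Do not import the Section 10.2 model whole. It includes the baseline outcome, and no baseline cardiac MRI is done.

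State that MPR is the sub-study's primary endpoint and that MP is supportive. This costs no alpha. Splitting alpha instead (0.025 each) would lower paired-t power for MPR to about 76%.

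The cost is SAP wording and one degree of freedom. If there is in fact no period effect, power is 84.8% at 9:9, 80.4% at 12:6 and 76.3% at 13:5, against 85% unadjusted. Make the change before unblinding, so that the choice cannot depend on the observed split or results.
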